5.9 Subject Replacement Strategy

5.10 Clinical Criteria for Early Trial Termination

Early trial termination will be the result of the criteria specified below:

1. Quality or quantity of data recording is inaccurate or incomplete
2. Poor adherence to protocol and regulatory requirements
3. Incidence or severity of adverse drug reaction in this or other studies indicates a potential health hazard to subjects
4. Plans to modify or discontinue the development of the study drug

In the event of Merck decision to no longer supply study drug, ample notification will be provided so that appropriate adjustments to subject treatment can be made.

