9.1 Data Set Descriptions

This study will utilize a standard 3+3 design and dose de-escalation will proceed according to the following scheme. Three doses of MK-3475 (100 mg, 150 mg, 200 mg) will be given to 3 different groups of 3 patients. If the toxicity is greater than 1/3 in one group then the next lower dose will be used. This will establish the MTD, if present. If more than 1/3 of patients experience DLTs at the lowest dose (70 mg), it will be concluded that MK-3475 cannot be given safely with chemo/radiation. If one of three patients at any dose level experiences grade 3 or greater toxicity then another 3 patient will be accrued at the same dose level. If 1/6 patients has grade 3 or higher toxicity then escalation will proceed, if 2/6 has grade 3 or greater toxicity then this is declared the MTD. If 3/6 has grade 3 or greater then we will reduce the dose level.

Part A: Is only for patients with Limited stage SCLC, we will allow induction chemotherapy.

Part A for LS-SCLC

Part B: Is only for patients with Extensive stage SCLC who are receiving consolidation XRT after 1-6 cycles of chemotherapy.

[figure not shown]

Table 1: Dose De-escalation, For Part A and B

Dose Level	MK-3475 (dose during XRT)	Toxicity Assessment	New MK 3475 dose
+2	200mg Q 3 weeks	If over 1/3 grade 3 toxicity is seen	150mg Q 3 weeks
+1	150mg Q 3 weeks	If over 1/3 grade 3 toxicity is seen If 0/3 grade 3 toxicity is seen	100mg Q 3 weeks 200mg Q 3 weeks
0 (starting dose)	100mg Q 3 weeks	If over 1/3 grade 3 toxicity is seen If 0/3 grade 3 toxicity is seen	70mg Q 3 weeks 150mg Q3 weeks
-1	70mg Q 3 weeks	If over 1/3 grade 3 toxicity is seen	We will conclude MK-3475 cannot be safely given after Chemo/radiation

Once the MTD is determined for each study part we will accrue at this MTD until we reach a total of 40 patients for each study part. Should DLTs occur in more than 1/3 of patients enrolled into this expanded cohort, dosing at that level will be stopped. A review of all DLTs observed will be conducted, and the need to lower the dose will be based on the discussion and agreement between

the IRB and the Investigator. Once at dose level +2, if 0/3 toxicity is seen we will not close the study for new patient enrollment until the third patient has passed the DLT assessment period, because even if this third patient has a DLT was seen it would no change the dose for future patients as another 3 patients at the same dose level would be needed.

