All patients who receive any MK-3475 will be considered evaluable for response and will be included in the efficacy data set.

DLT is defined as any:

- DLTs are defined as any adverse event(s) considered related to the combination of MK-3475 plus radiation as described below:
 - Any \geq Grade 3 bronchospasm or other hypersensitivity reaction;
 - Any other \geq Grade 3 non-skin related adverse event with the exception of laboratory abnormalities;
 - Any Grade 4 laboratory abnormalities, except AST, ALT, or total bilirubin;
 - AST or ALT $> 8 \times$ ULN,
 - Total bilirubin $> 5 \times$ ULN;
 - Any other Grade 4 adverse event;
- 1. Any adverse event, laboratory abnormality or intercurrent illness which, in the judgment of the investigator, presents a substantial clinical risk to the subject with continued study drug dosing;
- 2. Subject experiences an allergic/infusion reaction while receiving study drug at a slower infusion rate due to a prior allergic/infusion reaction;
- 3. Any motor neurologic toxicity \geq Grade 3 regardless of causality;
- 4. Any \geq Grade 3 treatment-related sensory neurologic toxicity.
- 5. Drug related toxicity that prevents administration of MK-3475 for > 21 days from the scheduled dose
 - The time frame for DLT assessment will be within 22 days of therapy initiation.
 - Any grade 4 neutropenia (with or without fever and/or sepsis) or thrombocytopenia (with or without bleeding) lasting at least 1 week or longer (as defined by the NCI-CTC v4.0).
 - Any other grade 3 non-hematologic toxicity including symptoms/signs of vascular leak or cytokine release syndrome; or any severe or life-threatening complication or abnormality not defined in the NCI-CTCAE v4.0 that is attributable to the therapy.

9.2.1. *Statistical Analysis*

Descriptive statistics will be computed for all relevant outcomes, including toxicity, tumor response, PFS, OS, and biomarker response. Descriptive analysis will include a global assessment of patient outcomes for parts A and B separately. All patients receiving at least 1 treatment with MK-3475 will be included in the analysis.

9.2.2. *Demographics and Baseline Characteristics*

Frequency distributions of gender and race will be tabulated by dose/cohort. Summary statistics for age, body weight, height, and Body Mass Index (BMI) will be tabulated by dose/cohort.

9.2.3. *Safety Analyses*

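### The expansion stop in 9.1 divides DLTs by patients enrolled, and the plan defines neither DLT-evaluable patients nor replacement, so incompletely observed patients can dilute the DLT fraction

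*Combined protocol and SAP*

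**What the plan says.** - **Expansion stop (9.1).** "Should DLTs occur in more than 1/3 of patients enrolled into this expanded cohort, dosing at that level will be stopped". The expansion runs on from the escalation: "we will accrue at this MTD until we reach a total of 40 patients for each study part". The size of the expansion alone is not given, nor is the time at which the fraction is examined.
- **DLT window (9.1, DLT definition).** "The time frame for DLT assessment will be within 22 days of therapy initiation".
- **Escalation rules (9.1).** After one event in three, "another 3 patient will be accrued at the same dose level". One in six escalates, three in six reduces, and "if 2/6 has grade 3 or greater toxicity then this is declared the MTD". Nothing says that the three or six patients must have been observed through the window.
- **Populations.** The only definition of evaluability is for response: "All patients who receive any MK-3475 will be considered evaluable for response and will be included in the efficacy data set". Section 9.2.1, on descriptive statistics, adds: "All patients receiving at least 1 treatment with MK-3475 will be included in the analysis". Section 9.0 requires evaluability data for every registrant but gives no criterion.
- **Replacement.** "5.9 Subject Replacement Strategy" is a heading with no text beneath it.
- **Observation after stopping treatment.** Section 7.2 records adverse events to 30 days after treatment ends. Section 7.1.5.3.1 requires a safety visit about 30 days after the last dose, or before new anti-cancer treatment if that comes first.

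**The concern.** A DLT fraction is meaningful only if each patient in the denominator has had the chance to show a DLT. *Enrolled* does not carry that meaning. As worded it takes in three kinds of patient without a complete result: those never dosed, those dosed but not yet at day 22, and those lost before day 22 without a DLT. Each raises the number of DLTs needed to stop and adds no evidence of safety.

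The 3+3 cohorts have a related gap. With no DLT-evaluable definition and no replacement rule, the handling of a patient lost before day 22 is left to whoever applies the rules. If that patient keeps a place as a non-DLT, the observed rate is too low.

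Safety and the MTD are the primary endpoint (4.2.3.1), and escalation decisions rest on three to six patients, so one such patient can change a decision.

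**Working it through.** **Plan's own figures.** The plan gives no operating characteristics for the 3+3 or for the expansion stop. The one probability in 9.2.5 (88% chance of at least one toxicity in 40 patients at a true rate of 0.1) does not reproduce: 1 − 0.9^40 = 98.5%, while 1 − 0.9^20 = 87.8%. That is a separate matter; nothing below depends on it.

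**1. Expansion stop at the boundary.** Dosing stops if DLTs / enrolled > 1/3.
- 7/20 = 35.0%: stop.
- 7/21 = 33.3%, exactly 1/3 and so not more than 1/3: continue.
- 7/22 = 31.8%: continue.

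Each enrolled patient without a complete result raises the bar by one third of a DLT.

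**2. Number of pending patients.** Section 9.2.5 plans about 1.5 patients per month over 26 months, and it is unclear whether that is per part or for both parts together. With 365/12 = 30.4 days per month:
- Per part (1.5 × 26 = 39, close to 40): 1.5 × 22/30.4 = 1.1 patients inside the window at a time.
- Both parts combined, split equally: 0.75 × 22/30.4 = 0.5.

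Patients enrolled but not yet dosed come on top of this.

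**3. 3+3 rules if unseen DLTs are scored as none.** The plan gives no rate of loss before day 22. Assume that 0%, 10%, 20% or 30% of DLTs go unseen and that those patients stay in the cohort as non-DLTs (worst case). With true risk 0.40 and loss d, the apparent risk is q = 0.40(1 − d). For one cohort of three:
- no DLT: c = (1 − q)^3
- one DLT: b = 3q(1 − q)^2
- two or more: a = 1 − b − c

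Then P(reduce) = a + b·a = a(1 + b), and P(escalate) = c + b·c = c(1 + b).

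| d | q | a | b | c | P(reduce) | P(escalate) |
|---|---|---|---|---|---|---|
| 0 | 0.40 | 0.3520 | 0.4320 | 0.2160 | 0.5041 | 0.3093 |
| 10% | 0.36 | 0.2955 | 0.4424 | 0.2621 | 0.4262 | 0.3781 |
| 20% | 0.32 | 0.2417 | 0.4439 | 0.3144 | 0.3489 | 0.4540 |
| 30% | 0.28 | 0.1913 | 0.4355 | 0.3732 | 0.2746 | 0.5358 |

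If exactly one of the first three patients is unobserved and fixed as a non-DLT, the other two give 0, 1 or 2 DLTs with probability 0.36, 0.48 and 0.16. Then P(reduce) = 0.16 + 0.48 × 0.352 = 0.329, and P(escalate) = 0.36 + 0.48 × 0.216 = 0.464.

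**4. Expansion stop under the same assumption.** Take an expansion of 31 patients (assumed), examined once at the end, with true risk 0.40. Stopping needs 11 DLTs (11/31 = 35.5%; 10/31 = 32.3%). A share d of patients leaves before day 22, unrelated to toxicity, with none of their DLTs seen.
- Enrolled denominator: P(Bin(31, 0.40(1 − d)) ≥ 11).
- Evaluable denominator: the mean over m ~ Bin(31, 1 − d) of P(Bin(m, 0.40) > m/3).

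| d | Stop, enrolled | Stop, evaluable |
|---|---|---|
| 0 | 75.5% | 75.5% |
| 10% | 59.1% | 73.9% |
| 20% | 40.3% | 72.4% |
| 30% | 22.9% | 70.6% |

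For the expansion sizes tried between 20 and 40 with d = 20%, the enrolled denominator gives 40% to 47% and the evaluable one 67% to 76%.

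**The case against.** A reader might infer that the plan scores early leavers as toxicity-free. It does not say so. The at-least-one-dose sentence in 9.2.1 sets the population for descriptive reporting and does not govern the 9.1 decisions. Section 9.0 also expects evaluability to be recorded. For the 3+3 cohorts the fair statement is that the handling is unspecified.

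A reader might also infer that every early exit hides a DLT. Most do not. A patient who only stops treatment is still followed under 7.2 to 30 days after treatment, which outlasts a 22-day window. Weekly physician visits during radiation (7.1.4.2) and the safety visit add to this. An intercurrent illness that the investigator judges a substantial risk with continued dosing is itself a DLT (9.1, item 1). What remains is mainly consent withdrawal, loss to follow-up, early unrelated death and early new therapy. The loss rates used above are therefore assumed and worst case.

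A third tempting inference is that fast enrolment alone could hold the fraction below 1/3 for long. At about 0.5 to 1.1 pending patients per part, the effect shifts the bar by a fraction of one DLT and ends when those patients reach day 22. Section 5.10, item 3, also allows termination for the incidence or severity of adverse reactions whatever the fraction.

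All three limits stand. None changes the denominator in the expansion rule, which is explicit and, for never-dosed and unobserved patients, permanently too large.

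**Conclusion.** The point holds in two parts of unequal strength.

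- **Expansion stop.** This is in the text. Applied as written, one enrolled patient without a complete result turns a stop at 7/20 into a continuation at 7/21. For pending patients it is a short delay; for the never-dosed and the unobserved it lasts.
- **3+3 cohorts.** This is a gap in the plan. With no DLT-evaluable definition and an empty 5.9, nothing prevents a patient lost before day 22 from being counted as a non-DLT.

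If such patients are counted that way, the direction is certain, because an unseen DLT can only lower the observed rate. The size is not known. At a true risk of 40% with 10%, 20% or 30% of DLTs unseen, P(reduce) falls from 50% to 43%, 35% or 27%, and P(escalate) rises from 31% to 38%, 45% or 54%. These figures assume that every such DLT is missed and that the patient keeps a place in the cohort. The documents support neither those loss rates nor a claim that this handling is planned.

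**What to change.** 1. In 9.1, define a DLT-evaluable patient as one who received at least one dose of MK-3475 and either had a DLT at any time in the window or was observed through day 22.
2. Use DLT-evaluable patients in place of patients enrolled as the denominator of the expansion stop.
3. Apply the same definition to the 1/3, 1/6, 2/6 and 3/6 rules.
4. State in 5.9 that non-evaluable patients are replaced within the 40-per-part cap.
5. Do not make radiation being under way a condition for counting a DLT. A DLT before radiation starts would then drop out, and the readable text does not fix the order of radiation and cycle 1.
6. Keep the at-least-one-dose set for adverse-event and efficacy tables. List non-evaluable patients with the reason and last day observed, since leaving them out assumes that their leaving was unrelated to toxicity.

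The cost is protocol wording and an occasional replaced patient within the same cap. One side effect should be known: at an interim look a DLT counts at once, whereas an event-free patient counts only from day 22, so the fraction leans slightly high for a short time. That error is on the cautious side.

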3.0 OBJECTIVE(S) & HYPOTHESIS(ES)

3.1 Primary Objective(s) & Hypothesis(es)

- (1) **Objective:** Safety of MK 3475 plus chemo/radiation for LS-SCLC and safety of MK 3475 plus radiation for ES-SCLC

Hypothesis: MK-3475 with chemoradiation for LS-SCLC and with radiation for ES-SCLC will demonstrate an acceptable toxicity profile comparable to previous trials

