4.2.3 Rationale for Endpoints

4.2.3.1 Efficacy Endpoints

Part A LS-SCLC: The primary endpoint is safety in order to establish the MTD of MK-3475 with concurrent chemo and radiation. The primary acute toxicity for chemo and radiation is esophagitis with a rate of $\geq 32\%$ ⁸. While the long term toxicity rate of grade 3 pneumonitis is around 13%⁹.

Part B ES-SCLC: The primary endpoint is safety in order to establish the MTD of MK-3475 with concurrent radiation. The primary acute toxicity for chemo and radiation is esophagitis with a rate of $\geq 32\%$ ⁸. While the long term toxicity rate of grade 3 pneumonitis is around 13%⁹.

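### The DLT definition shared by Parts A and B gives no single answer for a brief grade 4 cytopenia, does not settle whether chemotherapy-attributed toxicity counts in Part A, and is not the standard the dose rules use

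*Combined protocol and SAP*

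**What the plan says.** Section 9.1 defines DLTs once, for both parts. The list opens with the word any, followed by a lead-in: "DLTs are defined as any adverse event(s) considered related to the combination of MK-3475 plus radiation as described below". The items that bear on this point are:

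- **Laboratory line:** "Any Grade 4 laboratory abnormalities, except AST, ALT, or total bilirubin". It sets no duration and has no haematologic exception.
- **Grade 4 catch-all:** "Any other Grade 4 adverse event". It sets no duration either.
- **One-week line, lower in the list:** "Any grade 4 neutropenia (with or without fever and/or sepsis) or thrombocytopenia (with or without bleeding) lasting at least 1 week or longer".
- **Other attribution wording:** the motor neurologic item applies "regardless of causality". The sensory neurologic item requires a relation to treatment, the dosing-delay item a relation to drug, and the final item speaks of an event "that is attributable to the therapy", without saying which therapy.

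The objective in Section 3.1 is "Safety of MK 3475 plus chemo/radiation for LS-SCLC and safety of MK 3475 plus radiation for ES-SCLC". For Part A, Section 4.2.3.1 adds: "The primary endpoint is safety in order to establish the MTD of MK-3475 with concurrent chemo and radiation". Section 8.0 gives all Part A patients platinum and etoposide in 3-week cycles, and the DLT window is 22 days.

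The dose rules in Section 9.1 add three patients, escalate, declare the MTD or reduce according to toxicity of grade 3 or above. Table 1 there counts grade 3 toxicity. The term DLT appears in the rule for the 70 mg level and in the stopping rule for the expanded cohort.

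**The concern.** The DLT call is the primary endpoint in its working form. Three features prevent it from giving one answer per event.

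1. Two items without a duration limit and one with a limit cover the same event, and nothing says which governs.
2. The lead-in leaves out chemotherapy, although the Part A question and the conclusion drawn at 70 mg concern MK-3475 with chemoradiation. An investigator who attributes marrow toxicity to platinum/etoposide may drop it, and one who attributes it to the whole regimen may count it.
3. The escalation rules and Table 1 mostly use a grade threshold in place of the DLT definition.

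Each level holds 3 to 6 patients, so a different score for one patient can turn escalation into expansion, or a declared MTD into a reduction. The dose carried into the 40-patient cohort could then depend on the reading chosen. The first and third features affect both parts. The second matters mainly for Part A, because Part B has no concurrent chemotherapy.

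**Working it through.** **Text check.** Take a patient with grade 4 neutropenia lasting 3 days inside the 22-day window. Neutrophil and platelet counts are laboratory values in this protocol (Section 5.1.2, Table 1), and Section 7.2 treats an abnormal laboratory finding as an adverse event.

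| Provision applied | Does the event count? |
|---|---|
| Laboratory line, event judged related | Yes |
| Grade 4 catch-all, event judged related | Yes, if not already caught |
| One-week line, read as governing cytopenias | No, by implication |
| Lead-in, event attributed to chemotherapy only | No |
| Dose rules read literally (grade 3 or above) | Yes |

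**Consequence for one dose level.** The plan states no operating characteristics for its 3+3 rule, so there is no figure of its own to reproduce. From Section 9.1: 0/3 escalate; 1/3 add three; 1/6 escalate; 2/6 MTD; 2/3 or more, or 3/6 or more, reduce. For this illustration DLT stands in for the grade threshold in those rules.

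For a per-patient DLT probability p, let b0 = (1−p)³ and b1 = 3p(1−p)².

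- P(escalate) = b0 + b1·b0
- P(MTD) = b1²
- P(reduce) = (1 − b0 − b1)(1 + b1)

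Assumptions, none of them given in the documents: other DLTs occur at rate p0; brief grade 4 cytopenia that passes the attribution test occurs independently at rate q. If brief events count, p = 1 − (1−p0)(1−q); if not, p = p0.

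Worked case, p0 = 0.10, brief events not counted: b0 = 0.9³ = 0.729; b1 = 3 × 0.1 × 0.81 = 0.243; P(escalate) = 0.729 × 1.243 = 0.906; P(reduce) = 0.028 × 1.243 = 0.035.

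Worked case, p0 = 0.10, q = 0.30, counted: p = 1 − 0.9 × 0.7 = 0.37; b0 = 0.250; b1 = 0.441; P(escalate) = 0.360; P(reduce) = 0.446.

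| p0 | Quantity | Not counted | q = 0.10 | q = 0.20 | q = 0.30 | q = 0.40 |
|---|---|---|---|---|---|---|
| 0.10 | P(escalate) | 0.906 | 0.730 | 0.536 | 0.360 | 0.221 |
| 0.10 | P(reduce) | 0.035 | 0.130 | 0.275 | 0.446 | 0.617 |
| 0.32 | P(escalate) | 0.454 | 0.329 | 0.226 | 0.146 | 0.088 |
| 0.32 | P(reduce) | 0.349 | 0.481 | 0.610 | 0.727 | 0.825 |

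The second baseline borrows the esophagitis figure of at least 32% in Section 4.2.3.1. That section gives neither grade nor timing, so treating it as a DLT rate inside the window is itself an assumption.

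Reaching 200 mg from 100 mg takes two escalations. With p0 = 0.10 and the same rate at both levels, the probability is 0.906² = 0.82 if brief events do not count. If they count, it is 0.53, 0.29, 0.13 or 0.05 for the four values of q.

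**The case against.** The best defence is that the list is disjunctive. It asks for any one item, and the one-week line includes events without excluding any. No sentence says that a shorter grade 4 cytopenia is not a DLT, so on a literal reading the brief event counts if related, and the one-week line is merely redundant for it. This stands as far as it goes. A reader might infer that the plan expressly scores the event both ways, and it does not: the negative answer comes only by implication. But the literal reading leaves a deliberately written threshold without effect on the event it describes, and two careful investigators could still differ.

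A second defence is that the lead-in governs only the items directly beneath it, so the laboratory line covers events related to MK-3475 plus radiation and the one-week line covers prolonged cytopenia whatever its cause. That gives every line a function. The text does not say so, however, and the nesting of the list, as extracted from the PDF, cannot settle it.

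Third, a reader might infer that Part A fails to test whether MK-3475 worsens chemoradiation toxicity. The documents do not support that. Section 9.2.3 tabulates adverse events by grade, type and dose/cohort with no attribution filter, the investigator-judgment item names no causal agent, and the motor neurologic item ignores causality. Section 3.1 does not itself require chemotherapy-attributed events to be DLTs, and leaving them out of dose decisions could be a legitimate choice. What remains is that the plan does not state the choice.

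Finally, the probabilities depend on assumed rates. This is correct, and the swing is smaller in absolute terms at the higher baseline.

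**Conclusion.** The concern holds as an internal inconsistency in the definition behind the primary endpoint. The cytopenia conflict is in the shared list and affects both parts. The attribution gap concerns Part A: it is unclear whether toxicity attributed to chemotherapy counts. The use of a grade threshold in most of the dose rules is a third standard, under which a brief grade 4 cytopenia would count whatever the DLT list says.

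For size, counting brief events lowers the chance of escalating from a level from 91% to between 73% and 22% with other DLTs at 10%, and from 45% to between 33% and 9% with other DLTs at 32%. These figures illustrate sensitivity to the wording and do not predict what the trial will see. They rest on assumed rates, on independence, and on brief events passing the attribution test. The textual finding needs none of them.

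The documents do not show which haematologic or attribution rule was intended, and this review takes no position on that.

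**What to change.** Four edits to Section 9.1, with the haematologic and attribution rules chosen by the sponsor and investigator:

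1. Reconcile the laboratory line, the grade 4 catch-all and the one-week line together, so that each grade 4 neutropenia or thrombocytopenia has one answer. Adding an exception to the laboratory line alone would not be enough, because the catch-all would still capture brief events.
2. State for each part which treatment components an event must be related to, and which items that test governs, consistently with the objective in Section 3.1.
3. Make the escalation rules and Table 1 count the same event throughout, whether DLT or grade 3 or higher toxicity.
4. Re-score any cohort already assessed under the reconciled text.

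The cost is a few lines of protocol text and a re-read of DLT calls already made. The downside is that some dose levels may be judged differently after re-scoring.

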5.6.1.2 Supportive Care Guidelines for Pneumonitis

Subjects with symptomatic pneumonitis should immediately stop receiving MK-3475 and have an evaluation. The evaluation may include bronchoscopy and pulmonary function tests to rule out other causes such as infection. If the subject is determined to have study drug associated pneumonitis, the suggested treatment plan is detailed in Table 7.

Table 7 Recommended Approach to Handling Pneumonitis

Study drug associated pneumonitis	Withhold/Discontinue MK-3475?	Supportive Care
Grade 1 (asymptomatic)	No action	Intervention not indicated
Grade 2	Withhold MK-3475, may return to treatment if improves to Grade 1 or resolves within 12 weeks	Systemic corticosteroids are indicated. Taper if necessary.
Grade 3 and Grade 4	Discontinue MK-3475	Systemic corticosteroids are indicated. The use of infliximab may be indicated as appropriate. Refer to the Event of Clinical Interest and Immune-related Adverse Event Guidance Document for additional recommendations.

For Grade 2 pneumonitis that improves to \leq Grade 1 within 12 weeks, the following rules should apply:

- First episode of pneumonitis
 - May increase dosing interval by one week in subsequent cycles
- Second episode of pneumonitis – permanently discontinue MK-3475 if upon rechallenge subject develops pneumonitis \geq Grade 2

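### DLT criterion 5 (a dose delay of more than 21 days) is first met about day 44, after the 22-day DLT window has closed; secondarily, the dose rules do not name one counted event

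*Combined protocol and SAP*

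**What the plan says.** Section 9.1 of the combined protocol and SAP contains both the dose rules and the DLT definition.

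**Timing.** Numbered item 5 of the DLT list is "Drug related toxicity that prevents administration of MK-3475 for > 21 days from the scheduled dose". The bullet directly below it reads "The time frame for DLT assessment will be within 22 days of therapy initiation". MK-3475 is given every 3 weeks (Section 5.2, Table 2), on Day 1 of each cycle with an administrative allowance of 3 days either way (Section 5.2.2). No text dates item 5 by when the toxicity began, extends the window for it, or holds a cohort decision while a delay is running.

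**Other routes to a DLT.** The list includes any "Grade 3 non-skin related adverse event with the exception of laboratory abnormalities" at that grade or above, "Any Grade 4 laboratory abnormalities, except AST, ALT, or total bilirubin", AST or ALT above 8 × ULN, and bilirubin above 5 × ULN. It closes with "Any other grade 3 non-hematologic toxicity including symptoms/signs of vascular leak or cytokine release syndrome". Item 1 is a judgment clause: "Any adverse event, laboratory abnormality or intercurrent illness which, in the judgment of the investigator, presents a substantial clinical risk to the subject" if dosing continues.

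**Counted event.** Most dose rules are written in terms of grade 3 toxicity, for example "If 1/6 patients has grade 3 or higher toxicity then escalation will proceed". The 70 mg rule in the text and the stopping rule for the expansion cohort are written in terms of DLTs.

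**The concern.** Safety, in order to establish the MTD, is the primary endpoint of both parts (Section 4.2.3.1), and each dose decision rests on three to six patients. A DLT criterion that can only be met after the assessment period has ended cannot affect those decisions, although a reader of the list would think it does.

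The kind of event at stake is shown by Table 7 in Section 5.6.1.2. For Grade 2 pneumonitis the instruction is "Withhold MK-3475, may return to treatment if improves to Grade 1 or resolves within 12 weeks". Such a patient may be off drug for weeks in a trial of thoracic radiation, without a Grade 3 event that another bullet would count.

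The mixed vocabulary is a lesser problem of the same kind. Two people applying Section 9.1 to the same cohort should count the same events, and the wording does not guarantee that they will.

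**Working it through.** **1. When criterion 5 can first be met.** The 22-day window is a specified value with no formula behind it, so there is nothing to reproduce. Take day 1 as the first MK-3475 dose and as therapy initiation.

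- Dose 2 is due on day 1 + 21 = day 22.
- A delay of exactly 21 days falls on day 22 + 21 = day 43. A delay of more than 21 days is first true on day 22 + 22 = **day 44**.
- Gap after a window closing on day 22: 44 − 22 = **22 days**. If the window is read as 22 elapsed days, it closes on day 1 + 22 = 23 and the gap is 44 − 23 = 21 days.
- If dose 2 is moved by the 3-day allowance, it falls on day 19 or day 25, giving 19 + 22 = day 41 or 25 + 22 = day 47.

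Every variant is outside the window, and delays to later doses are met later still.

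**2. What is lost.** Non-laboratory, non-skin events of Grade 3 or higher that are attributed to treatment are DLTs under another bullet, whatever happens to dose 2. What remains is mainly lower-grade toxicity that prevents dosing. Grade 2 pneumonitis is the clear case: Table 7 allows up to 12 weeks (84 days) for recovery, so a hold of more than 21 days is well within what the protocol foresees. Without criterion 5, only item 1 can make it a DLT.

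**3. Which event each rule in Section 9.1 counts.**

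| Rule | Event counted |
|---|---|
| 1 of 3: add three patients | Grade 3 or greater toxicity |
| 1/6, 2/6, 3/6 decisions | Grade 3 or greater toxicity |
| Table 1, upper three rows | Grade 3 toxicity |
| 70 mg, text | DLTs |
| 70 mg, Table 1 row −1 | Grade 3 toxicity |
| Stop in the expansion cohort | DLTs |
| Closing sentence on level +2 | A DLT, under the add-three rule |

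**4. Where the two terms differ.** The main DLT list requires attribution to MK-3475 plus radiation; the grade 3 rules state no attribution. The list also leaves out Grade 3 laboratory values. The clearest instance is a Grade 3 hematologic value in Part A, where patients receive platinum and etoposide (Section 8.0). The non-laboratory bullet excludes it, the laboratory bullet starts at Grade 4, and the closing bullet is limited to non-hematologic toxicity. Table 3 in Section 5.2.1.2 does not hold MK-3475 for it. With one such patient in a cohort of three and item 1 not invoked, the count is 1/3 for grade 3 toxicity (add three patients) and 0/3 for DLTs (escalate).

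**5. Liver values.** Appendix 13.4, Section 3.5, places AST or ALT above 5 × ULN and bilirubin above 3 × ULN under Grade 3 events. The specific DLT cut-offs are 8 × and 5 × ULN. Values between these limits are not DLTs if the cut-offs govern, but may be DLTs if the closing bullet is read literally. The plan does not say which applies.

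**The case against.** On criterion 5, the best defense is that any team would count a toxicity that began inside the window and later led to a long delay. That is workable, and the fix adopts it. But the plan does not say it, and on that reading the patient's status is still unknown until day 44, with no instruction to wait.

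On the counted event, the defense is stronger. The last sentence of the text below Table 1 says that a DLT in the third patient at level +2 would call for three more patients. That is the add-three rule, written earlier for grade 3 toxicity, applied to a DLT. The 70 mg rule, written once with each term, also fits loose usage of one idea. This is good evidence that DLT was intended, and it makes the second point one of terminology. It does not alter the wording of the operative rules or the table.

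A reader might go further and infer that one cohort could be sent in opposite directions on liver values. With AST at 6 × ULN in two of three patients at 100 mg, the grade 3 count is 2/3 (go to 70 mg) and the DLT count is 0/3 (go to 150 mg). The documents do not support this as a general statement. It holds only if the liver cut-offs override the closing bullet and no investigator invokes item 1. Section 5.2.1.2 groups laboratory abnormalities with non-hematological toxicity, which favors the literal reading of the closing bullet. Appendix 13.4 advises discontinuing the drug above 5 × ULN, which makes item 1 a natural choice.

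**Conclusion.** The timing point stands. Criterion 5 is first met about day 44, some three weeks after DLT assessment ends, and as written it cannot inform a dose decision. This rests on counting day 1 as the first MK-3475 dose and on the 3-week schedule; the alternative counts above change the gap by days and never close it.

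The consequence is narrow. A reader might infer that severe toxicity escapes the dose rules or that the MTD will be biased. Neither follows: most events of Grade 3 or higher are counted under other bullets, item 1 remains available for the rest, and the documents give no rate for prolonged lower-grade toxicity from which to estimate a frequency or direction.

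The terminology point is secondary. DLT was probably meant throughout, but the rules and Table 1 do not say so, and the terms differ in attribution and for Grade 3 laboratory values. The status of intermediate liver values is an open question for the sponsor.

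**What to change.** 1. Reword item 5: a drug-related toxicity with onset within 22 days of therapy initiation is a DLT if it delays dose 2 by more than 21 days. Add that the cohort decision is held while such a delay is pending. Cost: an occasional wait of about three weeks (day 22 to day 44), only when a patient is off drug for this reason.
2. Use DLT as the counted event in every rule of Section 9.1 and in all four rows of Table 1 there. If DLT was the intent, this is wording only. The sponsor should confirm that, because Grade 3 laboratory values outside the DLT list would then clearly not count unless item 1 is invoked.
3. State whether the 8 × and 5 × ULN cut-offs or the closing bullet governs AST or ALT above 5 and up to 8 × ULN, and bilirubin above 3 and up to 5 × ULN. This is a clinical choice that can loosen or tighten the safety rule, so it belongs to the sponsor and no direction is proposed here.
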